#### Provider

After visit with the subject

- certainty, confidence, satisfaction (Appendix P)
- provider perception of care (Appendix N)
- provider global impression of change (Appendix O)

# Visits 1-6 (Group A receives test results at visit 3, Group B receives test results at visit 1)

Before visit with the provider

- DVPRS, PROMIS short forms for pain interference, depression, anxiety, BPI perception of pain relief item
- patient perception of care
- patient global impression of change

After visit with the provider

certainty, confidence, satisfaction

#### Provider

After visit with the subject

- certainty, confidence, satisfaction
- provider perception of care
- provider global impression of change
- provider usage (visit 6 only)

Table 1: Visit Chart

	Group A (Delayed)	Group B
Visit 0	Consent, saliva sample	Consent, saliva sample
Visit 1		Receive results
Visit 2		
Visit 3	Receive results	
Visit 4		
Visit 5		
Visit 6	Last visit	Last visit

At the end of the study patients' medications will be extracted from records and changes will be documented and analyzed. All opioids will be converted to oral morphine equivalents.

Protocol Title: Patient and provider confidence and satisfaction with the clinical use of CYP genetic variability analysis to guide analgesic treatment: A randomized, controlled pilot study using the Pain

Medication and Mental Health DNA Insight  $^{TM}\;\; test.$ 

Initial Date Submitted: 02/10/2015 Revision Date: 31 August 2016

#### 7.4 RISKS TO SUBJECTS:

There is little direct risk associated with the analysis of the patient's DNA. A patient will submit a saliva sample only, no invasive procedure is required. The sample will then be shipped to the testing site and results will be forwarded to the medical provider.

The only risk of data collection during the study is potential loss of privacy/confidentiality of enrollment in the study. The consent forms with the subject's name will be stored in a locked file cabinet in the research coordinator's office at WAMC. The master link between subject name and ID will be stored in a password protected excel file on the V drive at WAMC, with access limited to only the study team. This file will be separate from the file containing the collected data.

Analysis of personal genetic information potentially carries risk of future health insurance discrimination. The results of the DNA Insight Test will not become part of the patient's medical record and not be visible to potential future health insurers. While price discrimination based on genetic make-up is a theoretical risk, the nature of the information in the DNA Insight does not lend itself to discrimination by insurers.

As with any laboratory test, patients are exposed to the potential risk of results misinterpretation. In this case, misinterpretation could result in adverse medication effects up to and including death of the patient. When a clinician obtains test results, that clinician is expected to possess the appropriate knowledge and clinical judgment to accurately interpret the test and prudently act on those results. All primary care providers are trained on basic drug pharmacokinetics and pharmacodynamics during medical training. Primary care providers are expected to have knowledge of the CYP system and its genetic heterogeneities. Furthermore, primary care providers are expected to possess clinical judgment in deciding the appropriateness of specialty consultation. For this study, to address the potential risk of results misinterpretation, primary care providers will be provided with an information sheet reminding them of the availability of pain specialty consult. All analgesic dosing changes should be done with appropriate clinical judgment and prudence in accordance with standard of care for the practice of primary care medicine. Providers credentialed by Womack Army Medical Center are subject to this organization's strict and thorough credentialing process.

#### 8.0 DATA ANALYSIS:

For this two-group design, a variety of self-report measures (confidence, certainty, etc.) will be taken up to a maximum of 8 repeated measures, including a baseline measure prior to the intervention. Given this variability where time is not a fixed factor insofar there may be variation for number of measures by individual and/or group a mixed linear modeling (or sometimes referred

Protocol Title: Patient and provider confidence and satisfaction with the clinical use of CYP genetic variability analysis to guide analgesic treatment: A randomized, controlled pilot study using the Pain

 $\label{eq:medication} \mbox{Medication and Mental Health DNA Insight}^{\mbox{\scriptsize TM}} \ \ \mbox{test.}$ 

Initial Date Submitted: 02/10/2015 Revision Date: 31 August 2016

to by the umbrella term: multilevel modeling-MLM) analysis will be conducted. The advantage of a MLM approach is that it is sufficiently flexible insofar inter-individual variability on (1) time and (2) number of measures can be readily accommodated. Moreover, in the context of a longitudinal design interindividual differences in intraindividual trajectories can be captured.

When conducting a MLM analysis, the assumption is that there is a nested structure, and particularly for event-based studies, time (level 1-microlevel) will be nested within the patient (level 2- individual). For this study there are 12 provider groups with 4 patients nested within the groups, hence this could be cast as a 3-level model (time nested within patient nested within provider). However, one caveat is this is a very small sample size for MLM, and power may be a significant issue. The viability of increasing the sample size or aggregating levels (if deemed appropriate insofar it does not compromise the integrity of the design) will be explored. A sequence of models will be examined, with the unconditional means model (no predictors) as the starting point, serving to compute the unconditional intraclass correlation coefficient (ICC), and hence capturing the extent of between-patient variability. Subsequent models will entail adding a variable that captures time, and then at the macro-level introducing the grouping (experimental vs. control) variable. If deemed appropriate, all time-invariant and time-varying predictors will be testing for significance ( $\alpha = .05$ ) and moreover, the stochastic parameters (i.e., variance components) will also be examined:  $\underline{u}_0$  and possibly  $\underline{u}_1$  where  $\underline{u}_0$  is the random coefficient for the intercept (i.e. initial basis) and  $u_i$  is the random coefficient for the slope. For the single-item ordinal-level outcomes the cumulative logit link function will be employed using residual maximum likelihood (REML) as the default estimator (otherwise the identity link function will be used for continuously measured outcomes).

Selection of the best fitting model will be guided not only by the change in magnitude of the variance components, represented in part by the pseudo r statistic, but also information-theoretic indices such as the Akaike Information Criterion (AIC) or Bayesian Information Criteiron (BIC), of which the model with the lower value evinces better fit. All MLM analysis will be conducted using the HLM7.01 software. Data cleaning, testing of assumptions and descriptive analysis will be performed in SPSS v. 22 or Stata v. 11.0. Moreover, as a basis of comparison (again keeping in mind small sample size) generalized estimating equations (GEE) will also be considered, with an unstructured working correlation matrix stipulated as the error variance/covariance matrix (though alternatives such as autoregressive with lag 1 (AR1) may be considered).

As for testing concordance of patients and caretakers, correlations will be computed as well as intraclass correlation coefficients (ICC) so as to assess the level of relationship between the patients and providers on like-items.

Commented [1]: Can [name] address this sentence?

Protocol Title: Patient and provider confidence and satisfaction with the clinical use of CYP genetic variability analysis to guide analgesic treatment: A randomized, controlled pilot study using the Pain

Medication and Mental Health DNA Insight  $^{TM}\;\; test.$ 

Initial Date Submitted: 02/10/2015 Revision Date: 31 August 2016

References: See Section 6.1

A database will be created in REDCap (Research Electronic Data Capture) after IRB approval. REDCap is a secure, web-based application for building and managing online surveys and databases. The data will be housed and secured on Defense and Veteran Center for Integrative Pain Management (DVCIPM) servers. Each patient will be allocated a study ID number, 01-48 and providers will be assigned study ID numbers 101-112, when they sign a consent form, and thereafter will be referred to by that number in the database. Investigators and research staff will have secure password protected access to RedCap in order to enter data.

The REDCap data will be extracted and sent to an outside DVCIPM statistician, for analysis. PHI will be removed before sending to the statistician.

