# **7.2 SPECIFIC AIMS/SIGNIFICANCE:** Specific Aims

- 1. Examine trends in provider decisions in prescribing analgesics and modifying analgesic treatment plans and provider outcomes for satisfaction, certainty and confidence in dosing of analgesics with and without access to Pain Medication and Mental Health DNA Insight TM genetic testing results.
- 2. Examine trends in patients' satisfaction, certainty and confidence in dosing of analgesics between patient groups whose providers had access to Pain Medication and Mental Health DNA Insight TM genetic testing results and those whose providers did not have access to the genetic information.
- 3. Compare patient-reported pain and mental health outcomes between patient groups whose providers had early access to Pain Medication and Mental Health DNA Insight TM genetic testing results to those who had delayed access in the control period and subsequently following later access to the results.

The general aim of this pilot study is to assess the utility of a test that analyzes the DNA of chronic pain patients to determine their metabolic response to common analgesics, anti-depression and anxiolytic medications, to improve provider and patient confidence and satisfaction with the pain treatment plan. The results of the DNA analysis will help guide providers to change or continue the current analgesic regimen. This concept is known as "personalized" or "precision" medicine - the ability to treat patients based on their genetic profile in order to maximize therapeutic effect and minimize or eliminate unwanted side effects.

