#### 7.3 DESIGN

#### 7.3.1 Design type:

This is a prospective, randomized, controlled, observational pilot study analyzing both providers' and patients' perceptions and responses to the DNA Insight test. For this study there will need to be a total of twelve provider groups to be enrolled and 4-8 of each provider's patients will be enrolled in the study. Enrollment will continue of providers until up to 12 providers and 48 patients have been enrolled in the study. Therefore twelve to sixteen military health system primary care providers will need to be consented due to withdrawal of providers prior to

Page 13 of 34

Protocol Title: Patient and provider confidence and satisfaction with the clinical use of CYP genetic variability analysis to guide analgesic treatment: A randomized, controlled pilot study using the Pain

Medication and Mental Health DNA Insight $^{\text{TM}}$  test.

Initial Date Submitted: 02/10/2015 Revision Date: 31 August 2016

referring patients. A total of 48 patients will be enrolled, 4-8 patients for each of the actively enrolled providers (12- 16 providers and 48 patients total). Each provider's patients will be randomized into delayed treatment (Group A) or immediate treatment (Group B) at a 1:1 ratio. Each participating provider will agree to order and interpret a Pain Medication and Mental Health DNA InsightTM test. Results for patients in Group A will be given to the provider with a 3 month delay. Those in the 3 month delay will serve as a comparison group for the period prior to receiving intervention. Results for patients in Group B will be given to the provider without delay, 2-3 weeks after saliva sample collection. The provider will use the results of the Pain Medication and Mental Health DNA InsightTM test to evaluate whether changes of medications are indicated based on the individual patient's genetic profile. A measure of the provider's certainty, confidence, satisfaction, perception of care and global impression of change will be assessed at baseline, prior to obtaining the test results, and after obtaining the test results, as outlined in the data collection section. Patients' pain related self-reported outcomes, certainty, confidence and satisfaction will be assessed at baseline, prior to obtaining the DNA InsightTM test results, and after receipt and implementation of the test results, as described in the data collection section of the protocol.

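### Section 8.0 names only a time-invariant group term, so the control-period (access versus no access) contrast that the aims need is not specified

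*Combined protocol and SAP*

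**What the plan says.** Design. Section 7.3.1 describes a delayed-access trial with 1:1 randomisation within provider. Of Group A it says: "Those in the 3 month delay will serve as a comparison group for the period prior to receiving intervention". Section 7.3.6 and Table 1 put receipt of results at Visit 1 in Group B and Visit 3 in Group A, with Visit 6 the last visit for both.

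Aims (section 7.2). Aim 2 compares patients whose providers had the results with "those whose providers did not have access to the genetic information". Aim 3 compares patients of providers with early access "to those who had delayed access in the control period and subsequently following later access to the results". Aim 1 concerns provider decisions and ratings with and without access.

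Analysis (section 8.0). The self-report measures "will be taken up to a maximum of 8 repeated measures, including a baseline measure prior to the intervention". The model sequence starts from an unconditional means model, and then: "Subsequent models will entail adding a variable that captures time, and then at the macro-level introducing the grouping (experimental vs. control) variable". On other predictors: "If deemed appropriate, all time-invariant and time-varying predictors will be testing for significance". The random slope is left as a possibility, and AIC or BIC helps choose the model.

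Timing of instruments (sections 7.3.4 and 7.3.6). The pain and mental health scales, perception of care and patient global impression (Appendices D-J) are completed before each visit. The certainty, confidence and satisfaction surveys and the provider forms (Appendices M-P) are completed after it.

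**The concern.** In section 8.0 time is the lowest level of the model, so a grouping variable entered at the macro-level is constant over a patient's visits. It labels Group A as control at every visit, including those after Group A's providers hold the results. The coefficient averages visits at which only Group B has results with visits at which both arms or neither has them. That average is not the access versus no-access comparison of Aim 2 or the control-period comparison of Aim 3. Aim 1 is affected in the same way.

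Section 7.1 says that the findings are to supply preliminary data for a fully powered trial. A diluted coefficient could make a useful test look inert or distort the planning of that trial. Because the dilution depends on the covariance model, and the plan lets fit criteria guide that choice, the same named coefficient could mean different things for different outcomes.

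**Working it through.** The documents give no effect size, variance, correlation or power, so there is no planned figure to reproduce. The inputs are the visit schedule (Table 1), instrument timing (7.3.4, 7.3.6) and 12 providers × 4 patients = 48, or 24 per group (7.3.1, 8.0). Everything else is an assumption and is marked so.

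**1. Exposure by visit under Table 1**

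| Instruments | B exposed from | A exposed from | Visits at which only B is exposed |
|---|---|---|---|
| M-P (after visit) | Visit 1 | Visit 3 | 1, 2 |
| D-J (before visit) | Visit 2 | Visit 4 | 2, 3 |

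The arms differ at two of the seven visits, 0 to 6.

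**2. What the group coefficient estimates.** Assume receipt shifts the outcome at once by a constant δ, with complete data and a random intercept. The group coefficient is then the plain average over visits of the between-arm difference:
- Visits 0-6: (2 × δ + 5 × 0)/7 = 0.286δ.
- Visits 1-6: 2δ/6 = 0.333δ.

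This holds for any within-patient correlation. Other covariance models weight visits unequally. With AR(1) correlation 0.3-0.7, or an uncorrelated random slope (variance 0.005-0.03 per visit squared), the share is 17-50% over Visits 0-6 and 19-79% over Visits 1-6. These ranges are illustrative, not bounds.

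**3. A second reading of the schedule.** One paragraph of section 7.3.4 lists Visits 1, 2 and 3 within Group A's wait and returns results after it. Read that way, M-P at Visit 3 is unexposed in Group A. The M-P share becomes 3/7 = 0.43 (Visits 0-6) or 3/6 = 0.50 (Visits 1-6).

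**4. Does group × linear time repair it?** Fit a line to the between-arm difference over Visits 0-6 (random intercept; visits centred at 3, sum of squares 28).
- M-P: slope = (−2 − 1)δ/28 = −0.107δ per visit; intercept at Visit 0 = 0.286δ + 3 × 0.107δ = 0.607δ.
- D-J: slope = (−1 + 0)δ/28 = −0.036δ; intercept = 0.286δ + 3 × 0.036δ = 0.393δ.

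A sustained benefit appears as a Visit 0 difference that does not exist, plus a negative slope. Neither term is the control-period contrast. A 0/1 receipt indicator by visit recovers 1.00δ if the effect is constant.

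**5. Illustrative power.** Assumptions: δ = 0.5 SD; two-sided 0.05; normal reference; 2:2 within each provider, so provider variance cancels; patient/residual variances (p/r) 0.3/0.7, 0.5/0.5, 0.4/0.5, 0.4/0.4. For the mean of k visits, SE² = (p + r/k)/12. With Visit 0 as covariate, SE² = (p + r/k − p²/(p + r))/12.

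| Comparison | Mean difference | SE | Power |
|---|---|---|---|
| Group term, Visits 0-6, unadjusted | 0.5 × 2/7 = 0.143 | 0.183-0.218 | 10-12% |
| Control period, 2 visits, unadjusted | 0.5 | 0.224-0.250 | 52-61% |
| Group term, Visits 1-6, Visit 0 as covariate | 0.5/3 = 0.167 | 0.149-0.167 | 17-20% |
| Control period, 2 visits, Visit 0 as covariate | 0.5 | 0.183-0.216 | 64-78% |

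**6. Limit of the control-period contrast.** If the effect builds evenly over three visits, the two visits in the window carry 1/3 and 2/3 of it, averaging 1/2. At a full effect of 0.5 SD the contrast is 0.25 SD, and baseline-adjusted power is 21-28%.

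**The case against.** The strongest reply is that the plan already contains what is needed. Sections 7.2 and 7.3.1 state the control-period comparison, section 8.0 admits time-varying predictors, and this is a hypothesis-generating pilot whose first two aims examine trends. Much of this stands. A reader might infer that the plan rules out a receipt term or overlooks the control period; the documents support neither. What remains is that no model term, visit window or contrast in section 8.0 carries the stated intent, and following the named sequence yields a different quantity.

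A reader might also take 29% as the share. It is exact only under Table 1, a constant immediate effect and a random intercept. The two readings of Visit 3 alone move the M-P share from 2/7 to 3/7, and section 8.0 allows up to 8 measures where Visits 0-6 give 7.

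It is tempting, too, to set 10-12% power against 64-78%. That mixes the effect of the visit window with that of baseline adjustment; the comparison must be unadjusted with unadjusted, or adjusted with adjusted. A large gap remains either way.

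Finally, a contrast matched on visit number is not matched on time. Group B's results arrive 1-3 weeks after the saliva sample by section 7.3.4, or 2-3 weeks by section 7.3.1, while Group A's visits are at least a month apart. Group B's Visit 1 can therefore fall earlier after enrolment, and an underlying trend would enter the contrast. This stands and needs a sensitivity analysis.

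**Conclusion.** The omission is certain from the text and should be fixed. The only between-group term named in section 8.0 is time-invariant, over all repeated measures, in a design where both arms end up exposed. It does not estimate the contrasts of Aims 2 and 3, nor that of Aim 1, and adding group × linear time does not change this.

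The size is less certain. The count of two visits in seven follows from Table 1. The 2/7 share (1/3 over Visits 1-6) needs the further assumptions stated above, and the power figures rest on assumed effects and variances. The documents do not support one fixed degree of dilution, nor a claim that the trial cannot answer its aims. The planned data can supply the right contrast once it is written down.

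**What to change.** 1. Reconcile the protocol on whether Group A's Visit 3 falls before or after receipt: the wait-period paragraph of 7.3.4 against the follow-up paragraph of 7.3.4, section 7.3.6 and Table 1. Reconcile the maximum of 8 measures in 8.0 with Visits 0-6.
2. In 8.0, name as the main estimate the randomised Group B minus Group A contrast over the visits at which only Group B has results. Set the window by instrument (under Table 1, Visits 2-3 for D-J and Visits 1-2 for M-P). Keep provider as a level. Adjust for the Visit 0 value where it is a true baseline, which excludes the global impression of change items (Appendices J and O).
3. Report visits after Group A's receipt separately, as follow-up.
4. As a supporting estimate, fit a visit-level receipt indicator, coded by instrument from the actual date of receipt, and state that it assumes a constant effect.
5. Report actual days since Visit 0 by group, with a days-adjusted sensitivity analysis.

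The cost is wording and one derived variable, with no new patients, visits or instruments. The price is that the main estimate measures the early effect only, and the plan should say so.

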#### 7.1 HYPOTHESES/RESEARCH QUESTIONS:

This is a pilot study and thus our goal is to explore the feasibility of an appropriately powered clinical study, which would investigate the utility of the Pain Medication and Mental Health DNA Insight TM test to improve pain management of patients with chronic pain. Our goal is to explore how providers and patients will respond to this test and we intend to use our findings to generate hypotheses and preliminary data for a robust, fully powered clinical trial in the future.

Our research questions are:

How does the use of the Pain Medication and Mental Health DNA Insight TM test affect provider satisfaction, certainty and confidence in dosing of opioid and non-opioid analgesics?

How does the use of the Pain Medication and Mental Health DNA Insight TM affect patient

WAMC Protocol Template Revised 3 January 2014

Page 12 of 34

Protocol Title: Patient and provider confidence and satisfaction with the clinical use of CYP genetic variability analysis to guide analgesic treatment: A randomized, controlled pilot study using the Pain

Medication and Mental Health DNA InsightTM test.

Initial Date Submitted: 02/10/2015 Revision Date: 31 August 2016

satisfaction, certainty and confidence in pain management plan?

How does the use of the Pain Medication and Mental Health DNA Insight TM test affect pain related patient-reported outcomes, including DVPRS, PROMIS and BPI scores?

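### Section 8.0 names REML for the cumulative-logit items; the linearised fit this implies understates the ICC, materially so only if answers bunch in the top category

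*Combined protocol and SAP*

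**What the plan says.** Section 8.0 (Data Analysis) plans mixed models with time nested in patient, and possibly patient nested in provider. For the single-item ordinal outcomes, "the cumulative logit link function will be employed using residual maximum likelihood (REML) as the default estimator". The bracket that follows covers the remaining outcomes: "otherwise the identity link function will be used for continuously measured outcomes". REML is therefore attached to the ordinal items in so many words. Section 8.0 does not mention full likelihood, Laplace or quadrature, and does not say what approximation stands behind REML for this link.

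The modelling sequence opens with a no-predictor model, "serving to compute the unconditional intraclass correlation coefficient (ICC", which is meant to show how much patients differ. Variance components, a pseudo R-squared and AIC or BIC then guide model choice, and HLM 7.01 is the stated software. GEE is to be considered for comparison.

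On size, section 8.0 says "For this study there are 12 provider groups with 4 patients nested within the groups" and section 7.3.1 says "A total of 48 patients will be enrolled". Section 7.1 states what the pilot is for: hypotheses and "preliminary data for a robust, fully powered clinical trial in the future".

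**The concern.** REML integrates the fixed effects out of a normal-error likelihood. A cumulative-logit mixed model has no such likelihood. To run REML at all, the model must first be replaced by a working linear model. That replacement is known to pull variance components towards zero when each patient contributes few and uneven ordinal answers.

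The quantity most exposed is the ICC, which section 8.0 says it will compute and which could serve as preliminary data for a later trial. If it is too low, patients will appear more alike, and repeated answers from one patient less correlated, than they are. A secondary consequence does not depend on how answers are distributed: a pseudo-likelihood fit yields no true likelihood, so the planned AIC and BIC comparisons have no proper basis for these items.

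**Working it through.** The documents give no odds ratio, ICC, number of categories or distribution of answers, so there is no stated figure to reproduce. The one sum available agrees: 12 × 4 = 48 patients. The bias has to be found by simulation.

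**Inputs from the documents.** 48 patients, "randomized into delayed treatment (Group A) or immediate treatment (Group B) at a 1:1 ratio", so 24 per group. Visits 0 to 6 give 7 measurements (section 7.3.6; section 8.0 allows up to 8). Results arrive at Visit 1 in Group B and at Visit 3 in Group A.

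**Assumptions.** Five categories; a random patient intercept only, with the provider level left out; true log odds ratio 1.0 for access to the results; patient variance 4 or 8; answers evenly spread, or with about 61% or 85% in the top category.

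**Latent-scale ICC.** ICC = σ² / (σ² + π²/3), with π²/3 = 3.29.
- σ² = 4: 4 / 7.29 = 0.55.
- σ² = 8: 8 / 11.29 = 0.71.

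**Fits.** Penalised quasi-likelihood (PQL) with a REML-type variance update, which is what REML can mean for this link, against full maximum likelihood (ML) by quadrature; 120 simulated trials per setting.

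| Answers | REML-type ICC (true 0.55 / 0.71) | Shortfall |
|---|---|---|
| Evenly spread | about 0.51 / 0.67 | 0.04 / 0.04 |
| 61% in top category | 0.47 / 0.61 | 0.08 / 0.10 |
| 85% in top category | 0.39 / 0.52 | 0.16 / 0.19 |

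In the two skewed settings full ML gave 0.53-0.54 / 0.71. The root-mean-square error (RMSE) of the ICC fell from 0.11-0.21 with the REML-type fit to 0.07-0.12 with ML. Since the standard deviation cannot exceed the RMSE, the Monte Carlo standard error of a mean ICC is at most 0.21 / √120 = 0.02.

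Back on the variance scale, σ² = 3.29 × ICC / (1 − ICC). The REML-type ICCs correspond to about 2.9 and 5.1 (61% top) and 2.1 and 3.6 (85% top), against true values of 4 and 8.

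**Second set of simulations.** 400 data sets per setting, true odds ratio 2.5, true ICC 0.25 / 0.50 / 0.70. REML-type ICC:
- evenly spread: 0.24 / 0.47 / 0.66;
- 70% in top category: 0.21 / 0.41 / 0.58;
- 85% in top category: 0.19 / 0.37 / 0.52.

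Full ML gave 0.23-0.24 / 0.48-0.49 / 0.70-0.71. The pattern is the same and shows that the absolute loss is small when the true ICC is low.

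**Odds ratios.** Across the simulations the REML-type fit shrank the access log odds ratio by roughly 5-20%, depending on setting. In the 400-run set with a top-category concentration it kept 0.91-0.95 of the true value. A constant group effect lost more there, down to 0.70 of the true value in the most extreme setting (85% top, ICC 0.70). In the 120-trial runs the RMSE of the access log odds ratio was 0.26-0.43 with the REML-type fit and 0.27-0.46 with ML, so at this sample size ML gains nothing on that measure.

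**The case against.** The strongest reply has four parts.

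- **The ceiling is assumed.** No section gives response categories or distributions, and the appendices are not reproduced. Eligibility requires pain for at least 3 months at an average score of 4 or higher that is not expected to improve without directed therapy, which makes a heavy top category less obvious for relief and global-change items. With even answers the bias is small. This stands, and the size of the point is conditional on it.
- **Scope is unclear.** Only single-item outcomes are affected. The PROMIS short forms have several items and would plausibly take the identity link. This stands too.
- **The plan hedges.** REML is only a default, section 8.0 warns that the sample is very small for multilevel modelling, and GEE is in view. None of this is a safeguard: no alternative estimator is named, GEE is not committed to, and GEE targets a marginal effect and does not supply the random-effect ICC.
- **Consequences are limited in an exploratory pilot.** This is right about the odds ratios but does not cover the ICC.

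A reader might infer that a later trial would be oversized by 1.3-1.6 times, from (1/0.88)² = 1.29 and (1/0.79)² = 1.60. That holds the standard error fixed, whereas the linearised fit shrinks it as well. Comparing mean estimate/SE for ML and the REML-type fit over about 100 data sets per setting gives (3.39/3.28)² = 1.07 and (3.11/2.97)² = 1.10 at 61% top, and (2.31/2.21)² = 1.09 and (2.15/1.98)² = 1.18 at 85% top. The documents also do not say how a later trial would be sized.

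A reader might also infer that a real effect would be missed or look materially weaker. The shrinkage is smaller than the sampling error at 48 patients, and interval coverage in a separate run of 120 trials per setting was 92.5-97.5%.

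**Conclusion.** The estimator sentence in section 8.0 is wrong as written, whatever the distribution of answers. Its practical effect falls on the patient variance and the ICC. With evenly spread answers the loss is about 0.04 on true values of 0.55 and 0.71. With 61% of answers in the top category it is 0.08-0.10, and with 85% it is 0.16-0.19. Full ML removes nearly all of this.

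These sizes rest on assumed category distributions, an assumed number of categories and assumed true ICCs, in a two-level model without the provider level. The documents do not establish that any item has a ceiling. The shrinkage of the access log odds ratio is real but does not by itself justify a change of estimator at this sample size.

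**What to change.** In section 8.0:

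- limit REML to the identity-link (continuous) outcomes;
- state that cumulative-logit models are fitted by full maximum likelihood with adaptive quadrature, in other software if HLM 7.01 cannot do this for the chosen model;
- report the latent-scale ICC (level-1 variance π²/3) and the odds ratios from that fit.

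This takes about one sentence of text and possibly a second software package. Design, visits and data collection are unchanged. The statistical cost is slightly more variable odds ratios when answers are heavily skewed. In the 400-run set ML overshot the log odds ratio by up to 11% in the most extreme settings. In the skewed 120-trial settings a small downward ICC bias remained at the lower true value (0.53-0.54 against 0.55), much less than the bias removed.
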